## 2.8 Home Hemodialysis Training

It is anticipated that 4 - 6 weeks will be allotted for home hemodialysis training during the baseline phase, although patients will be able to take more time, if needed, to complete the training process. During the training period, patients will receive hemodialysis treatments three times per week. All patients in the trial will initially be trained in the generic requirements for home hemodialysis. These processes include the following major tasks:

- 1) Vital signs, including BP measurement
- 2) Setting up and tearing down the dialysis machine without assistance
- 3) Recognizing machine problems and troubleshooting them appropriately
- 4) Able to access dialysis vascular access consistently and independently
- 5) Machine disinfection
- 6) Water treatment maintenance

At the end of the training process for generic home HD, the study coordinator will ascertain that the patient is still willing to be randomized to either conventional three times per week home HD or nocturnal daily home HD. If the patient is willing to be randomized, then the randomization protocol below will be implemented. After randomization, patients randomized to either arm of the study will receive additional training that is specific to the assigned home HD modality. It is anticipated that this additional training will take approximately one to two weeks.

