### 8.3 Data Collection and Methods

Resource use for patients assigned to either arm of this study will be assessed under the various headings, and by the methods listed in the tables below. Additionally, the following data will be available for economic and other analyses:

- Baseline income and employment status
- Follow up income and employment status
- Baseline vascular access
- All follow up vascular access replacement, repair or removal
- Home modification costs for nocturnal study patients

*General.* To obtain estimates of cost independent of year and geographical differences, we will denominate the use of resources initially in terms of more basic units: hours of nursing or other professional time, outlier adjusted DRG weights for hospitalizations and Medicare allowable charges for other types of payments, specific classes of equipment needed for dialysis and actual supplies used, actual non-injectable drug prescriptions. These will then be given dollar values using consistent references such as published salary scales, national average payments for diagnosis related groups (DRGs) for hospital services and relative value units (RVUs) for professional services, General Services Administration (GSA) contract prices, Red Book average wholesale prescription prices or Average Sales Price (ASP).

Resource use for patients assigned to either arm of this study will be assessed under the various headings, and by the methods listed in the Tables 10 - 13 below.

Cost element	Method of assessment	Calculation of standard cost
Training		
Nursing/technician time for training.	Expert judgment and personnel records of the directors of the home training centers.	Published salary scales for hands-on time/% hands-on time. Range of % hands-on time used for sensitivity assessment.
Professional time by other professional personnel: dietitians, social workers, etc.	Record of visits and times spent at same subset of dialysis sessions.	Published salary scales.
Equipment at each dialysis station	Generic list compiled by consensus of dialysis administrators.	GSA price list, with amortization period determined by consensus. Cost per dialysis will be computed.
Consumable supplies per dialysis	List will be assembled by Cost Subcommittee.	GSA price list.
Routine laboratory tests included in "bundle."	Published charges by large reference laboratories.	Inflation adjusted average published permitted charge.

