Overhead	Average overhead from CMS cost reports.	Applied as a percent to total of above.
Home dialysis itself		
Nursing technician time for clinic visits and troubleshooting	Expert judgment and personnel records of the directors of the home training centers.	Published salary scales for hands-on time/% hands-on time. Range of % hands-on time used for sensitivity assessment.
Professional time by other professional personnel: dietitians, social workers, etc.	Record of visits and times spent at same subset of dialysis sessions.	Published salary scales.
Equipment at each dialysis station	Generic list compiled by consensus of dialysis administrators.	GSA price list, with amortization period determined by consensus. Cost per dialysis will be computed.

Table 10:	Center Costs per	Dialysis of Home	Hemodialysis (3 or	6 Times Weekly):
	- · · · · · · · · · · · · · · · · · · ·			

Consumable supplies per dialysis	List will be assembled by Cost Subcommittee.	GSA price list.
Routine laboratory tests included in "bundle."	Published charges by large reference laboratories.	Inflation adjusted average published permitted charge.
Overhead	Average overhead from CMS cost reports.	Applied as a percent to total of above.

Table 11: Patient Costs per Dialysis of Home Hemodialysis (3 or 6 Times Weekly	Table 11: Patient	Costs per Dialy	vsis of Home Hemo	odialysis (3 or 6	Times Weekly)
--	-------------------	-----------------	-------------------	-------------------	---------------

Cost element	Method of assessment	Calculation of standard cost
Home modifications	Data from form 101 and form 260	Accrue to training costs, otherwise TBD.
Unreimbursed costs (phone line, estimated costs of electricity and water, etc.	Periodic costs data	Accrue to maintenance costs, otherwise TBD.

Cost element	Method of assessment	Calculation of standard cost
Injectable medicines given in dialysis units or at home for nocturnal hemodialysis patients.	Data from Forms 203 and 204 collected at baseline, F4, F8 and F12.	Medicare allowable charges for the various agents and doses.
Hospitalizations (Part A)	Estimated from claims for Medicare primary patients in study cohort. Record of ICD9 Diagnostic and Procedure Codes (or Canadian equivalent) and length of stay for all hospitalizations for patients in Medicare HMOs and Canada.	Consistent assignment of DRGs for each hospitalization (with duration adjustment), using "DRG grouper" and related standardized CMS payments.

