utilities and associated incremental cost effectiveness ratio (ICERs) with 95% confidence intervals. Acceptability Curves will be constructed to determine the probability of nocturnal hemodialysis being cost-effective over the standard hemodialysis under certain cost-effectiveness thresholds. Conventionally, ICERs of less than \$50,000 per QALY are considered very cost-effective whilst those with an ICER of between \$50,000 and \$100,000 per QALY are considered moderately cost-effective

In addition, the estimates from physician reported utilizations will be incorporated for sensitivity analysis.

- c) **Time-frame for analysis**: The economic evaluation will consider two time-frames: a) within trial one-year period, and b) the lifetime of the patient. We recognize specifically that the costs of the non-dialysis component of care may decline over the year of observation, such that the average over the year might underestimate the long-term impact on costs (and benefits). This will be assessed by estimating total costs within the first and the final four months of the study. We shall use a probabilistic economic model to project long-term survival, health benefits, and costs beyond the study period and extend the findings to patients and facilities not included in the trial. Lifetime costs and benefits will be **discounted at a rate of 3%**.
- d) Objective 1 Costs of dialysis: Costs per month of dialysis for patients in the two study arms will be determined by summing the per dialysis costs of dialysis as listed in Table 10 - 11 above and multiplying this sum by the average number of outpatient dialysis sessions per month for the patients in each arm of the study. This analysis may be useful to CMS and other payers in setting appropriate payment rates for nocturnal hemodialysis.
- e) **Objective 2 Total CMS covered costs**: Costs per month of CMS covered care will be summed by summing the average per month costs of dialysis (as in (d) above) and of other covered care as in Table 13 above.

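### Section 8.4(c) sets out to check for a decline in non-dialysis cost but compares total cost, which in section 8 also contains dialysis cost

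*Protocol*

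**What the plan says.** Protocol section 8.4(c) covers the time-frame of the economic evaluation. It notes that "the costs of the non-dialysis component of care may decline over the year of observation", and that an average over the year might then understate the long-term effect on costs. The check it sets is: "This will be assessed by estimating total costs within the first and the final four months of the study".

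Section 8.4(e) shows what a total contains in this evaluation. Total covered cost per month is formed by "summing the average per month costs of dialysis (as in (d) above) and of other covered care". Under 8.4(d), the dialysis part is the sum of the per-dialysis costs in Tables 10 and 11 multiplied by the average number of outpatient sessions per month in each arm.

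Table 10 includes a training block, beginning with "Nursing/technician time for training". For home modifications, Table 11 gives the rule "Accrue to training costs, otherwise TBD".

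On the timing of training, section 2.8 says: "It is anticipated that 4 - 6 weeks will be allotted for home hemodialysis training during the baseline phase". After randomization, "patients randomized to either arm of the study will receive additional training that is specific to the assigned home HD modality", and "It is anticipated that this additional training will take approximately one to two weeks".

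**The concern.** The question and the measure sit in adjoining sentences and concern different quantities. The question is about non-dialysis cost. The measure is a total that, in the section's own usage, adds dialysis cost to it.

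The check exists to show whether the yearly average misstates the longer-term picture. Section 8.1 hypothesizes that savings in non-dialysis care will offset the extra dialysis expense of nocturnal treatment. A movement in dialysis cost that is read as a movement in non-dialysis cost would bear directly on that hypothesis, in either direction.

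**Working it through.** The protocol states no cost figure for this check, so there is no figure to reproduce. I read the two windows as months 1-4 and 9-12 of each patient's follow-up.

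**Identity.** Let T be total cost in a window, D dialysis cost and N non-dialysis cost. Then T = D + N, and the change between windows is ΔT = ΔD + ΔN. The check reports ΔT, while the question is ΔN. They agree only if ΔD = 0.

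**Ways in which ΔD need not be zero, from the protocol:**

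- *Training after randomization (2.8, 2.9).* About 1-2 weeks in both arms, with no upper limit. Generic training of 4-6 weeks comes before randomization. The part after randomization is therefore between 1/(6+1) = 14% and 2/(4+2) = 33% of planned training weeks. A four-month window has 4 × 365.25/12/7 = 17.4 weeks, so this training takes up 1/17.4 = 6% to 2/17.4 = 11% of the first window.
- *Patients randomized to nocturnal under version 2.1 (2.2.1).* They were randomized before home training began, so their full training falls after randomization. They are few, and they stay in their assigned arm (8.4(a), 9.4).
- *Start-up laboratory tests (3.4.1(d)).* Nocturnal patients have calcium and phosphorus measured weekly for one month, every two weeks for one month, then monthly. With four-week months that is 4 + 2 = 6 occasions in two months against 2 on a monthly schedule, or about 4 extra, all early.
- *Step-down in frequency (3.1.6).* Nocturnal patients who cannot sustain six sessions may go to five or four. If the 8.4(d) product is formed within each window and per-dialysis cost is held fixed, such a patient's dialysis cost falls by 1/6 = 16.7% or 2/6 = 33.3%. With d the dialysis share of that patient's total cost, the total falls by d/6 or d/3 while non-dialysis cost has not moved. The protocol does not give d.

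**Illustration for a one-off cost.** Assume flat recurring cost and a one-off dialysis cost C, in months of recurring cost, booked when incurred in the first window. The apparent fall in total cost is C/(4 + C). The values of C are assumptions:

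| C (months) | Apparent fall |
|---|---|
| 0 | 0% |
| 0.25 | 5.9% |
| 0.5 | 11.1% |
| 1 | 20.0% |
| 2 | 33.3% |

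The between-arm difference shifts by C(nocturnal) − C(conventional), which is zero when the arms carry equal one-off costs.

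**After the fix.** With N compared directly, C and the session-count term drop out. Under flat non-dialysis cost the comparison shows no change, whatever their values.

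**The case against.** A reader might infer something stronger: that the first window carries the training and home set-up costs, so a fall appears by construction, is larger in the nocturnal arm, and flows into the lifetime projection. The documents do not support this, for five reasons.

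- **Timing.** By planned weeks, 67% to 86% of training precedes randomization under the current protocol. Home modification needs are assessed in baseline (2.7).
- **Costing.** Tables 10 and 11 are per-dialysis costs, multiplied by sessions under 8.4(d). Costed that way, training is spread over sessions, and with equal session counts both windows carry the same load. Equipment, which would include the nocturnal safety devices, is amortized. No passage says that training is booked to the months in which it occurs.
- **Arms.** Both arms have the same anticipated 1-2 weeks of training after randomization. The extra nocturnal laboratory tests are a real asymmetry but a small one.
- **Size.** Any assumed start-up share, or split of it between arms, lies outside the documents.
- **Use.** Section 8.4(c) does not say that the lifetime model takes this contrast as an input. Nursing time for training and home support is already a named sensitivity parameter in 8.4(b).

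All of this stands, and it rules out the stronger reading. It can also be argued that total costs here means the total of the non-dialysis component. The wording does not exclude that, but 8.4(e) uses total to include dialysis cost, and 8.4(f) lists dialysis costs and total CMS costs as separate items. Booking rules are commonly left to an analysis plan, so their absence is not the point. The point is that the measure named differs from the quantity in question, and varying a training parameter does not repair that.

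**Conclusion.** The mismatch holds: 8.4(c) asks about non-dialysis cost and names a measure that, as section 8 uses the term, includes dialysis cost. A change in dialysis cost can therefore appear as a change in non-dialysis cost, or mask one.

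The size and between-arm direction cannot be computed from the documents. They depend on unit costs that the protocol does not give, on whether one-off costs are booked when incurred or spread per session, and on whether session counts are taken within each window. The percentages for C are illustrations under assumed values and include zero.

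The point is minor. It touches one check within the secondary economic evaluation and leaves the co-primary outcomes unaffected.

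**What to change.** In 8.4(c), state that the comparison of months 1-4 with months 9-12 is made by arm on the non-dialysis component, meaning the items in the table titled *Other CMS Covered Medical Care*. Refer to that table by title, because two tables are numbered 13. Report dialysis cost as a separate line in each window, with training, home modification and start-up laboratory cost shown within it. If any of the start-up tests are classified as other covered care, move them to that line so that they do not enter the comparison.

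This needs no new data, since the components are already tabulated separately. The cost is a change of wording and a little more analysis.

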## 3.2 Duration of Treatment and Follow-up

Each patient will be treated in his/her respective group for 12 months, or until death, recovery of renal function or a stop-point is met (transplant, change to peritoneal dialysis, relocation to a nonstudy center – see Section 7.3). Except for those subjects who are transplanted, change to peritoneal dialysis, or die, data collection and follow-up will continue for all patients for a minimum of 12 months. For patients who relocate to a non-study dialysis unit or transfer to home hemodialysis during their 12 months of follow-up, all attempts will be made to collect vital status, the two coprimary outcomes (see Section 3.1), and the centrally administered quality of life questionnaires. When possible, the complete data collection procedures designated in the protocol will be maintained for subjects who switch to in-center HD. Those patients who are transplanted or switch to peritoneal dialysis will no longer be followed. Otherwise, no matter what happens to a patient, it is recommended that all attempts be made to encourage any subject who misses the two co-primary outcomes to provide these data for up to six months past his or her F12 window. Patients who need to switch from home HD to in-center HD due to an acute complication, new comorbid medical condition(s), patient or partner burnout or patient desire will continue to be followed in his/her respective group. Re-evaluation of each of these patients will be performed at regular intervals to determine if the patient is able and willing to restart home HD therapy. Adverse events hospitalizations and serious adverse events should be recorded for an additional 30 days after the patients' F12 month ends. Starting with the first dialysis session held at least 30 days after the patients' F12 month ends, one week of data should be recorded from the dialysis unit's run sheets. This data will include start time, end time, and pre and post weight and blood pressure for each dialysis session held during the week.

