### 8.2 Purpose

If nocturnal home hemodialysis proves to be effective in improving health outcomes, it will be important to understand:

- a) The changes in dialysis center costs to provide this mode of hemodialysis,
- b) The changes in overall health care costs to insurers (principally CMS) of patients using this mode of hemodialysis,
- c) The cost-effectiveness of the intervention (change in insurer costs per change in quality adjusted life-years)
- d) Costs per month for in-center hemodialysis (three times per week) obtained from the Daily Trial will be used to compare the monthly costs of nocturnal home hemodialysis with 3 times per week in-center hemodialysis.

The purpose of the economic analysis in this trial is to provide answers to these questions.

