#### 8.4 Analysis

- a) **Intention to treat**: All analyses will be performed on an "intention to treat" basis. That is, the average costs of patients in each arm will be determined retaining all patients in their originally randomized arm, irrespective of the treatment that is ultimately used for that patient. If a patient is lost to the trial by death, transplantation, withdrawal of consent, or move to a non-participating center, that patient will be included in his/her original randomization group, but the costs will be pro-rated for the actual time in the trial.
- b) **Sensitivity analysis**: An important component of any economic evaluation is an analysis of the uncertainty surrounding the differences in expected costs and expected utility of the alternative strategies. Our approach to the analysis of uncertainty will be informed by the guidelines of the Panel on Cost-Effectiveness in Health and Medicine (Gold et al, 1996):
  - Conduct univariate (one-way) sensitivity analysis for all variables to determine where uncertainty about some key parameters could have a substantial impact on the conclusions. A tornado diagram will be used to sort the variables by their magnitude of effect (sensitivity). The potential major sensitive parameters include rate of hospitalization, cost for a hospital stay, EPO dose and rate of EPO use, nursing time devoted to training and home support, proportion of home nocturnal to all dialysis patients, and various techniques to allocate overhead to each modality. For the lifetime analysis, additional sensitive parameters include technique survival (length of time on randomized modality), patient survival, and discount rate.
  - Conduct multivariate (2- or 3-way) sensitivity analysis for important parameters. This explores potential magnitude of effect when two or more key parameters are altered together. The results from univariate sensitivity analysis will serve as a guide to select the variables in multivariate sensitivity analysis. The potential sensitive parameters pairs may include hospital costs and rate of hospitalizations, or EPO dose and rate of EPO use.
  - Construct a confidence or credible interval around the cost-effectiveness result. Bootstrap simulation with replacement will be utilized to derive costs and

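### Section 8.4(d) prices every outpatient session at a home-hemodialysis unit cost, although patients dialyzing in-center stay in their randomized arm

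*Protocol*

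**What the plan says.** Section 8.4(d) defines monthly dialysis cost in two steps: "summing the per dialysis costs of dialysis as listed in Table 10 - 11 above", then "multiplying this sum by the average number of outpatient dialysis sessions per month for the patients in each arm of the study". The multiplier is not split by place of dialysis.

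The unit costs are for home treatment. Table 11 is titled "Patient Costs per Dialysis of Home Hemodialysis (3 or 6 Times Weekly"), and Table 10 has the same scope. Table 10 has a training block and a block headed "Home dialysis itself", with staff time taken from home training centers. Table 11 holds home modifications and household running costs. Neither table has an in-center block.

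Section 8.4(a) costs all patients in their original arm, "irrespective of the treatment that is ultimately used for that patient". It pro-rates costs only for death, transplantation, withdrawal of consent or a move to a non-participating center.

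Section 3.2 provides that "Patients who need to switch from home HD to in-center HD due to an acute complication", new comorbidity, burnout or preference stay in follow-up in their own group. Section 2.2.1 lets controls randomized in-center under version 2.1 remain in-center. Section 9.4 pools them with the home controls and estimates that more than half will transfer home.

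The one in-center cost in the plan is in Section 8.2(d): "Costs per month for in-center hemodialysis (three times per week) obtained from the Daily Trial will be used to compare the monthly costs". The comparison there is between in-center dialysis and nocturnal home dialysis, and Section 8.4(d) does not use the figure.

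**The concern.** The two factors in the 8.4(d) product cover different sets of sessions. The session count includes all outpatient dialysis in the arm, while the unit cost describes home dialysis alone. Any in-center session by a retained patient is therefore charged for home items and not for the staff, station and overhead of an in-center unit.

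This is a stated formula, not a detail left open. Its result is carried into total CMS cost in 8.4(e). In 8.4(f) it helps decide whether nocturnal dialysis is reported as improving outcomes at lower cost or through an incremental cost-effectiveness ratio. The cost comparison is part of the trial's implementation objective (Section 2.1, objective 7).

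**Working it through.** The protocol gives no cost figure, unit cost or expected switching rate, so there is nothing to reproduce. The check first sets the provisions side by side and then illustrates the scale.

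**Do in-center sessions enter the product?** Yes. 8.4(a) retains the patients and does not pro-rate for an in-center switch. Section 3.2 continues their follow-up, with complete data collection when possible. In-center maintenance sessions are outpatient sessions. If the multiplier were instead read as home sessions only, in-center dialysis would carry no dialysis cost, which conflicts with 8.4(a) more sharply.

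**Does another provision reprice them?** No. The Daily Trial cost in 8.2(d) serves a separate comparison of modalities. Time on the randomized modality is named as a sensitivity parameter for the lifetime analysis only.

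**Scale.** Inputs:

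- Sessions per month from the protocol schedules: nocturnal 6 × 52/12 = 26; conventional 3 × 52/12 = 13. In-center dialysis is taken as three times weekly, also 13.
- q, the share of an arm's patient-months spent in-center: assumed 5%, 10%, 20%.
- r, the in-center cost per session divided by the home cost per session: assumed 0.75, 1.5, 2.0.
- The home cost per session is set to 1 in both arms, also an assumption.

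With s = 26 or 13:

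- Plan as written: s(1 - q) + 13q
- Priced by place: s(1 - q) + 13qr
- Error = (plan as written / priced by place) - 1

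Example, conventional arm, q = 20%, r = 2: 10.4 + 2.6 = 13.0 against 10.4 + 5.2 = 15.6, so 13.0/15.6 - 1 = -16.7%. At r = 0.75: 13.0 against 10.4 + 1.95 = 12.35, so +5.3%.

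| Arm | q | r = 0.75 | r = 1.5 | r = 2.0 |
|---|---|---|---|---|
| Nocturnal | 5% | +0.6% | -1.3% | -2.5% |
| Nocturnal | 10% | +1.3% | -2.6% | -5.0% |
| Nocturnal | 20% | +2.9% | -5.3% | -10.0% |
| Conventional | 5% | +1.3% | -2.4% | -4.8% |
| Conventional | 10% | +2.6% | -4.8% | -9.1% |
| Conventional | 20% | +5.3% | -9.1% | -16.7% |

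**Difference between arms.** Subtracting the two arms, plan as written minus priced by place equals -13(r - 1)(qN - qC) home-session equivalents per month, where qN and qC are the nocturnal and conventional shares. This is zero when qN = qC. For qN = 20%, qC = 5%, r = 2: -13 × 1 × 0.15 = -1.95, that is 10.4 against 12.35, or -15.8%.

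| qN / qC | r = 0.75 | r = 1.5 | r = 2.0 |
|---|---|---|---|
| 5% / 5% | 0% | 0% | 0% |
| 10% / 5% | +1.4% | -2.7% | -5.3% |
| 20% / 5% | +4.9% | -8.6% | -15.8% |
| 5% / 10% | -1.3% | +2.7% | +5.6% |

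**The case against.** The best defense is one of scope. This is an economic objective, partly meant to inform payment for nocturnal dialysis, for which a home price is informative. Section 2.2.1 expects the legacy controls to be a small fraction. Section 3.1.6 steps non-adherent nocturnal patients down to five and then four sessions a week, so leaving the full schedule need not mean going in-center. Section 8.4(b) plans one-way sensitivity analysis on all variables, and 8.4(h) makes sensitivity analysis a major focus. This limits the likely size. It does not repair the formula: the within-trial calculation contains no in-center unit cost, so there is none to vary.

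Four stronger readings are tempting, and the documents do not support them.

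- **That technique failure falsely looks like a saving.** A nocturnal patient who moves in-center goes from about 26 sessions a month to about 13. That is a true fall in resource use, which intention-to-treat costing should show. Only the price is wrong. At r = 1.25 to 2, correct pricing gives 13r = 16.25 to 26 home-session equivalents against 26, so a saving remains at every r below 2.
- **That the error favors nocturnal dialysis.** This needs both r above 1 and more in-center time in the nocturnal arm. The documents give neither, and legacy in-center controls would act the other way.
- **That 5% of sessions is the protocol's own estimate.** The 5% implied by Sections 4.1 and 9.11 counts patients not completing modality-specific training. They need not go in-center. If they did, in the nocturnal arm they would contribute 0.65 of 25.35 sessions, or 2.6%.
- **That control patients' home injectables are left out.** The row "Injectable medicines given in dialysis units or at home for nocturnal hemodialysis patients" is loosely worded, but Section 8.3 assesses resource use in either arm, and the medication schedule has no arm restriction.

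**Conclusion.** The point holds as a specification error in the economic analysis. Followed as written, 8.4(d) gives in-center sessions a home unit cost, and no other provision corrects this before the figure enters 8.4(e) and 8.4(f).

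Its size and direction cannot be fixed from the documents. The range of about +5% to -17% for an arm's mean dialysis cost rests entirely on the assumed shares (5-20% of patient-months) and cost ratios (0.75-2.0). The arm difference is unaffected when in-center patient-months and home unit costs are the same in both arms. Otherwise it is generally wrong, in either direction. The efficacy analyses, including both co-primary outcomes, are untouched.

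**What to change.** In 8.4(d), count each patient's outpatient sessions by place of dialysis. Price home sessions at the Table 10-11 unit cost for the schedule followed, price in-center sessions at an in-center unit cost, and average within arm afterwards. The in-center cost can come from the Daily Trial figure already planned in 8.2(d), divided by the sessions per month it covers, because that section gives it per month. Carry the result into 8.4(e) and 8.4(f) unchanged.

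The cost is a few sentences and one input already due to be obtained, with two small burdens. Place of dialysis is not among the listed run-sheet items, so it must be derived from the discontinuation and modality-change records. The in-center cost also comes from a different trial population, which 8.4(g) calls not directly comparable, so it should be varied in the within-trial sensitivity analysis.
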